### 5.2 REPORTING PROCEDURES

Depending on the nature of the event the reporting procedures below should be followed. Any questions concerning adverse event reporting should be directed to the Chief Investigator in the first instance.

#### 5.3.1 Non-Serious AEs

The adverse events listed below are expected to be related and should be reported:

- GCS-related complications during admission (e.g. discomfort, skin breaks, skin ulcers, skin necrosis, blistering of the skin, rash, limb ischaemia)
- Bleeding complications during admission or within 24 hours of discharge
- Adverse reaction to LMWH during admission (e.g. rash or skin change, allergic reaction, thrombocytopenia, abnormal liver enzyme tests)

**Please note this is not an exhaustive list, if you suspect an event is related to treatment please contact the Trials Unit.**

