The VTE risks need to be balanced against the risks of preventative measures, both mechanical and pharmacological. Patient experience of stockings in the 'real world' is poor. In particular, the use of GCS is known to be associated with a number of undesired effects for the patient, including discomfort, ischemia, rolling down and creating a constrictive band, blistering. Previously, national stroke guidelines on VTE prevention extrapolated from small trials showing that GCS reduce the risk of DVT (6). The large randomised CLOTS 1 trial found no significant difference in symptomatic or asymptomatic femoro-popliteal DVT in individuals admitted to hospital with acute stroke (6). Importantly, CLOTS 1 also identified that skin breaks, ulcers, blisters, and skin necrosis were significantly more common in patients allocated to GCS than in those allocated to avoid their use (6). The widespread use of GCS has already been challenged and (3,4) limited in certain contexts, for example stroke patients. In view of the efficacy of GCS as an adjunct to LMWH in VTE prevention in surgical patients being poorly defined, GCS being responsible for complications and the enormous healthcare costs associated with their use, sufficient uncertainty is achieved to conduct a trial to examine whether GCS further reduces VTE incidence in surgical patients receiving prophylactic dose LMWH. There remains (despite guidelines) some variation in practice across the UK. We are aware of one centre, Salisbury District Hospital, which over the past three years has adopted a pharmacological prophylaxis policy (without GCS) that has been used for high risk surgical patients (n=249). In Salisbury, the incidence of hospital-acquired thrombosis is 1.3-2.9 per 1000 admissions, which is comparable to centres elsewhere in the UK (Kings College Hospital 3.83 per 1000 admissions) (34). As such, both patients and the health service stand to benefit from evidence to support the safe rationalisation of the use of GCS as a health technology. In this trial, all participants will receive effective thromboprophylaxis in the form of low dose (prophylactic rather than therapeutic) LMWH. This pharmacological strategy is used exclusively for groups where GCS are already contraindicated (for example peripheral arterial disease) or where evidence-based guidelines do not recommend their use (for example stroke patients (6)). A

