### 1.3 RATIONALE FOR CURRENT TRIAL

The aim is to determine whether low dose low molecular weight heparin (LMWH) alone is non-inferior to a combination of graduated compression stockings (GCS) and low dose LMWH for the prevention of venous thromboembolism (VTE) adult elective surgical inpatients identified as being at moderate and high risk for VTE. The primary clinical objective is to compare the VTE rate in elective surgical inpatients receiving GCS and LMWH, compared with LMWH alone.

The primary health economic objective is to calculate the cost-effectiveness with regards the use of GCS in addition to prophylactic dose LMWH in elective surgical patients identified as being at moderate and high risk for VTE. Other objectives include:

- To determine the experience of surgical patients receiving LMWH and those receiving both GCS and LMWH.
- To profile the adverse effects of GCS and LMWH anticoagulation in this context.
- To support future guidance and policy in VTE prevention.

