### 3.2.3.2 Secondary outcome measures

Generic quality of life will be assessed at baseline, upon discharge and at follow-up (both 14-21 days and 90 days) using the EQ-5D. EQ-5D is widely used and well validated, and is currently employed as part of the routine collection of Patient Reported Outcome Measures (PROMs) for the NHS in England (43).

Compliance with stockings will be addressed; participants will be issued with a VTE diary where they can document their GCS use, as well as any adverse outcomes related to GCS or LMWH use.

Compliance with LMWH will be assessed by review of the participant's medication chart by the local research nurse or study coordinator.

Mortality will be recorded however, it is anticipated that this will be very low.

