### *3.2.3.3 Safety outcome measures*

GCS-related complications, bleeding complications and adverse reactions to LMWH will be determined by review of medical notes and participant-reported comments in their VTE diary.

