## APPENDIX 1 SUMMARY OF INVESTIGATIONS, TREATMENT AND ASSESSMENTS

Timepoint	Estimated Duration (mins)	Computer Randomisation	Clinical Evaluation a	Duplex Imaging	Participant VTE Diary	EQ-5D	Stocking Compliance	Safety / Complications Monitoring b
Baseline (at the time of admission for elective surgery)	60							
During admission				If suspicion				
7 days post surgery OR At discharge c	60			If suspicion				
14 to 21 days post surgery	60						If not previously collected	
90 days post surgery	60			If suspicion				

a. Demographic details (age, sex, ethnicity), Pregnancy test for woman of childbearing age . General clinical details (body mass index, comorbidities, medication history, VTE symptoms and signs).

b. GCS- related lower limb complications / Bleeding complications / Allergic reactions to LMWH

c. Whichever occurs first

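### Non-serious leg and skin harms are defined as stocking-related, so they can describe harm in stocking wearers but cannot be compared by allocation without bias

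*Protocol*

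**What the plan says.** Section 5.3.1 introduces the reportable non-serious events with "The adverse events listed below are expected to be related and should be reported". The leg-harm item reads "GCS-related complications during admission (e.g. discomfort, skin breaks, skin ulcers, skin necrosis, blistering of the skin, rash, limb ischaemia"). A note adds that "this is not an exhaustive list, if you suspect an event is related to treatment please contact the Trials Unit". The other two items are bleeding, which carries no attribution, and adverse reactions to LMWH, whose examples include rash or skin change.

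The attribution label recurs elsewhere:

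- Section 3.2.3.3: "GCS-related complications, bleeding complications and adverse reactions to LMWH will be determined by review of medical notes and participant-reported comments in their VTE diary".
- Section 3.2.3.2: participants use the VTE diary to record stocking use "as well as any adverse outcomes related to GCS or LMWH use".
- Appendix 1, footnote b, on safety monitoring: "GCS- related lower limb complications / Bleeding complications / Allergic reactions to LMWH".
- The Trial Summary lists stocking-related complications among the safety outcomes.

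The stated objective (section 1.3) is "To profile the adverse effects of GCS and LMWH anticoagulation in this context". Section 1.2 cites a large stroke trial in which skin harms "were significantly more common in patients allocated to GCS than in those allocated to avoid their use".

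**The concern.** Both arms have surgery, and both can develop skin damage, leg discomfort or an ischaemic limb for reasons unrelated to stockings. To estimate how much of this is due to stockings, a randomised trial counts the same events in both arms and takes the difference. An outcome defined as caused by the stocking replaces that difference with a case-by-case judgement of cause, and the judgement requires knowing whether a stocking was worn. The trial is open. Section 4.1.1 undertakes that knowledge of allocation should not bias outcome assessment, but the blinding measures in section 6.5 concern imaging and do not reach this outcome.

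What is at stake is the harm side of the trial's message. Section 1.1 says any benefit of stockings must be weighed against their disadvantages, and the Impact section expects that dropping them would remove their side effects. If the final report sets stocking-related complications side by side by arm, readers will take the difference as a randomised estimate of avoidable harm.

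**Working it through.** The protocol states no figure on this point, so there is none to reproduce. The check is first textual, then a bounding illustration.

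**1. Which routes count non-serious leg events in the LMWH-alone arm?**

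| Route | Reaches LMWH-alone arm? | Cause-neutral count of non-serious leg events? |
|---|---|---|
| Leg-harm item, 5.3.1 | Only if stockings are worn | No: attributed to stockings |
| LMWH reaction item, 5.3.1 | Yes, both arms receive LMWH | No: attributed to LMWH; of the leg items, only rash or skin change overlaps |
| Catch-all note, 5.3.1 | Yes | No: needs suspected relatedness |
| SAE reporting, 5.3.2 | Yes | No: serious events only |
| AE collection at visits 1 and 3 (6.2, 6.4) | Yes | Not as written: 5.3.1 sets which non-serious events are reported |
| VTE diary (3.2.3.2, 6.1) | Yes: only the compliance diary is limited to the stocking arm | No: described by relation to stockings or LMWH |
| Notes review, 3.2.3.3 | Yes | Could be, but is directed at the attributed categories |

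No route asks for blisters, skin breaks, ulcers or discomfort in both arms whatever the cause. The bleeding item in the same list shows that the protocol can define a harm without attribution.

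**2. What does the attributed count estimate?**

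Let n be the number per arm, b the background risk of such an event, d the true excess from stockings, and a(S) and a(L) the proportions of events labelled stocking-related in the stocking and LMWH-alone arms.

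Expected recorded difference = n × [(b + d) × a(S) − b × a(L)]

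The causal excess is n × d. With a(L) = 0, the two agree only if a(S) = d / (b + d), that is, only if staff and participants attribute the correct share of events to the stocking. If d = 0, the recorded difference is n × b × a(S), which is false excess. If a(S) is too low when d is above zero, the excess is understated.

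**3. Upper bound with no true effect**

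Inputs: subpopulation 4 target 912 (7.1.2), allocated 1:1 (2.1), so n = 912 / 2 = 456. Assumptions not in the protocol: b as tabulated, d = 0, a(S) = 1, a(L) = 0. The p-values are from Fisher's exact test.

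| b (assumed) | 456 × b | Recorded | p |
|---|---|---|---|
| 0.5% | 2.3 | 2 v 0 | 0.50 |
| 1% | 4.6 | 5 v 0 | 0.06 |
| 2% | 9.1 | 9 v 0 | 0.004 |
| 3% | 13.7 | 14 v 0 | 0.0001 |
| 5% | 22.8 | 23 v 0 | <0.001 |

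If only half of the background events in the stocking arm were attributed to the stocking, 2% to 5% would give 456 × 0.02 × 0.5 = 4.6 to 456 × 0.05 × 0.5 = 11.4 events against 0.

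**The case against.** The strongest reply has four parts.

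- **The LMWH-alone arm is not silent.** Serious skin or limb events are reportable in both arms, rash or skin change can be recorded as an LMWH reaction in either, and the VTE diary and notes review are not restricted by arm. Section 8.2 leaves clinicians free to depart from allocation, so an LMWH-alone participant given stockings could have a stocking-related event. A reader might infer that leg harms are recorded only in the stocking arm. The documents do not support that. What remains is that none of these routes gives a cause-neutral count of non-serious leg events.
- **The objective is to profile.** A descriptive profile in stocking wearers meets it, and the protocol states no between-arm test of leg harm. It would therefore be wrong to say that the objective cannot be answered. The non-inferiority margin is justified in section 7.1.1 by what clinicians would tolerate and by the effect preserved, not by stocking harm, so the primary analysis is untouched. The loss is confined to a comparison by allocation.
- **The numbers are assumed.** This stands in full. The background rates come from no document, and complete attribution in one arm with none in the other is the extreme case.
- **The case report form, diary and SAP are not shown, and the change comes late.** The form may record leg events neutrally, but the protocol text fixes the attributed definition. Section 3.2.3.3 names the data sources, not who judges cause. Section 1.2 reports only the stroke trial's result by allocation, so it does not show how that trial recorded skin events. Appendix 3 has subpopulation 4 recruited and followed until April 2019, so new wording in a protocol dated December 2018 reaches only the last participants. This limits the benefit of the fix but does not remove the need to label the existing counts.

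**Conclusion.** The point holds in a limited form. Non-serious discomfort, skin breaks, ulcers, necrosis, blistering and limb ischaemia are defined by attribution to a device allocated to one arm. Collected as the protocol describes, they can profile harm in stocking wearers but cannot give an unbiased contrast by allocation. Serious events and skin reactions attributed to LMWH remain recordable in both arms.

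The size of the bias is unknown. The 9 to 23 against 0 is an upper bound resting on an assumed 2% to 5% background rate, full attribution in the stocking arm and none in the other. It shows that the definition alone could produce a nominally significant difference, not that it has done so. The conclusion also assumes that the unseen forms follow the protocol wording.

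**What to change.** In sections 3.2.3.3 and 5.3.1 and in Appendix 1 footnote b, replace the stocking-related item with *lower-limb skin or limb complications, whatever the suspected cause*. Record it in both arms on the same form at the same visits, keep attribution to stockings as a separate field, and report by allocation. The Trial Summary and the description of the diary in 3.2.3.2 need matching words.

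For participants recorded under the present wording, use the notes review already planned in 3.2.3.3 to recover events in both arms where it can. Report results by period, and state that attribution-based counts are descriptive and not a randomised comparison.

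The cost is the rewording of an existing item, a few more non-serious events to record, and two definitions across periods, with the neutral one covering only late recruits.

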### 5.3.2 Serious AEs

All SAEs should be reported. An SAE form should be completed and entered into the trial website within 24 hours. However, hospitalisations for elective or urgent treatment of a pre-existing condition do not need reporting as SAEs. In the event that the trial website is not available the Trial Manager should be notified by telephone, fax or email.

### 5.3.3 Reporting responsibilities of the CI

When an SAE form is uploaded onto the trial website, the Trial Manager will be automatically notified and will notify the Sponsor within 24 hours of receiving the signed SAE notification. The Sponsor will review all reported SAEs. A Sponsor cannot downgrade an assessment from the PI or CI. Any disparity will be resolved by further discussion between these parties.

If all the required information is not available at the time of reporting, the Investigator must ensure that any missing information is provided as soon as this becomes available. It should be indicated on the report that this information is follow-up information of a previously reported event.

All SAEs should be reported to the research ethics committee where in the opinion of the Chief Investigator, the event was:

- 'related', i.e. resulted from the administration of any of the research procedures; and

- 'unexpected', i.e. an event that is not listed in the protocol as an expected occurrence

Reports of related and unexpected SAEs should be submitted within 15 days of the Chief Investigator becoming aware of the event, using the NRES SAE form for non-IMP studies. The Chief Investigator must also notify the Sponsor of all SAEs.

Local investigators should report any SAEs as required by the, Sponsor and/or Research and Development Office.

## 6. ASSESSMENT AND FOLLOW-UP

Please refer to Appendix 1 for a summary of the trial-related visits.

### 6.1 BASELINE VISIT

Once consented, participants will undergo detailed clinical assessment by the research nurse as part of the baseline evaluation. Recorded assessments will include:

- Demographic details (age, sex, ethnicity)
- Pregnancy test for woman of child bearing age
- General clinical details (body mass index, comorbidities, medication history)

Additional assessments will include:

- EuroQuol 5D (EQ5D) generic quality of life assessment

At this point, eligible participants will be randomised 1:1 via the trial website to either:

- Current 'standard' combined low dose LMWH with GCS mechanical thromboprophylaxis, or
- Low dose LMWH pharmacoprophylaxis alone

The participant will be given further materials including:

- Participant VTE diary
- GCS compliance diary (GCS trial arm only)
- Participant contact and reminder card
- LMWH reminder card

And will proceed to their elective surgery as planned. Women of child bearing age will have another pregnancy test on the day of surgery if there is a possibility of pregnancy since the last test.

Post operatively the participant will be reviewed clinically as per standard care. This will include vigilance for the VTE.

## 6.2 FOLLOW-UP VISIT 1

The participant will be either seen in person at 1 week after surgery or at discharge (whichever is earlier). Recorded assessments will include:

- Any diagnosis of VTE (Anonymised copies of any duplexes will be forwarded to the Study Coordinating Centre at Imperial College London)
- Any symptoms or signs of VTE (if there is clinical suspicion identified by the research nurse which has not been identified by the clinical team, the research nurse will inform the clinical team who will proceed to imaging if appropriate).
- EuroQuol 5D (EQ5D) generic quality of life assessment
- Review of participant diary (completed until discharge)
- Collection of stocking compliance diary
- Collection of Adverse or Serious Adverse Events

If participant have been discharged without being assessed they will be contacted at either 1 week or as soon as possible.

## 6.3 FOLLOW-UP VISIT 2

All randomised participants will undergo a routine bilateral full lower limb duplex ultrasonography between 14 and 21 days post operatively to identify VTE. An anonymised copy of the duplex will be collected and forwarded to the Study Coordinating Centre, Imperial College London. We expect to capture >95% of VTE since the average time-point for DVT is seven days and PE is 21 days, with vast majority events being DVT. The range of dates is to prevent restricting scanning to a single date. EuroQuol 5D (EQ5D) generic quality of life assessment will also be administered at this visit.

## 6.4 FOLLOW-UP VISIT 3

Participants will be seen in person or contacted by telephone or online (according to participant preference) at 90 days post surgery.

Recorded assessments will include:

- Any diagnosis of VTE (Anonymised copies of any duplexes will be forwarded to the Study Coordinating Centre, Imperial College London)

- Any symptoms or signs of VTE (if there is clinical suspicion identified by the research nurse which has not been identified by the clinical team, the research nurse will inform the clinical team who will proceed to imaging if appropriate).
- EuroQuol 5D (EQ5D) generic quality of life assessment
- Review of participant VTE diary (completed until 90 days)
- Collection of Adverse or Serious Adverse Events

If clinical VTE confirmed on investigation at any point within 90 days, this will be recorded

- Symptomatic DVT
- Asymptomatic DVT identified by duplex
- Imaging-confirmed symptomatic PE

Any participant with asymptomatic (or symptomatic) DVTs identified by duplex ultrasound will proceed to being treated as per local guidelines for the management of DVT.

## **6.5 BILATERAL FULL LOWER LIMB DUPLEX ULTRASONOGRAPHY – BLINDING**

If participants are inpatients at the time of their routine bilateral full lower limb duplex ultrasonography at between 14 days and 21 days postoperatively, or if any inpatient duplex imaging is prompted by clinical suspicion, the research team will ensure that the GCS will be removed prior to imaging to ensure optimum blinding of those undertaking the imaging (9). The participant contact / reminder cards will also include a statement to remind participants to do this.

Maintaining the integrity of the blinding is a key consideration for all those involved in the trial, as compromising the blinding may have a significant impact on the interpretation of the results. We will ensure that measures are put into place that prevent deliberate or accidental unblinding. The blinding is particularly important in relation to the undertaking of imaging for the components of the primary endpoint. Clearly defined and communicated procedures for the prevention of unblinding will be implemented, which will target (i) imaging professionals, (ii) other healthcare professionals and (iii) the participant. Healthcare professionals caring for enrolled patients on the surgical wards will be requested to ensure that participants who have been randomised to receive GCS have these removed prior to leaving the ward for imaging. The healthcare professionals and the participants will be requested not to disclose which trial arm the participant is enrolled into to the imaging professionals. The imaging professionals – who are not part of the usual clinical team caring for the participants – will be instructed not to ask the participant or any accompanying

healthcare professional which trial arm the participant has been randomised to. The iDMC will be given information on any unintentional unblindings as the trial progresses, to assess whether there are training issues generally or at specific sites that need addressed. With these procedures in place, unintentional unblinding of the imaging staff should be minimised, and hopefully lowered to zero. We will explicitly ask the imaging staff for each individual randomised whether they were aware of the randomised treatment allocation, or thought that they were aware,

## **6.6 DEFINITION OF END OF PARTICIPANTS PARTICIPATION**

The end of the participants participation is defined as 90 days from the date of the index elective operation.

## 7. STATISTICS AND DATA ANALYSIS

### 7.1 SAMPLE SIZE

#### 7.1.1 ORIGINAL SAMPLE SIZE- APPLICABLE UP TO JANUARY 2018

With a one-sided test at 2.5% level of significance (equivalent to a 2-sided test at 5%) the trial has 90% power to conclude that the single pharmacological intervention is non-inferior to the combined intervention (pharmacology and stockings) assuming an event rate of 6% of VTE at 90 days in the combined group and a non-inferiority margin of 3.5%, and a conservative loss to follow up (i.e. non-evaluable for the primary outcome) rate of 10%. The maximum sample size required under this group sequential design, including allowance for loss to follow up, is a total of 2236.

We assume that the standard of care gives a VTE at 90 days proportion of 6%. Historically, we believe the systematic review supports an untreated rate of at least 15%. We have set the non-inferiority margin at 3.5% (i.e. a pharmacological alone rate under the null hypothesis of not more than 9.5%). We think this is justifiable on the grounds that clinicians would not tolerate more than a 3.5% absolute deterioration in VTE event rate over combination therapy, and that it preserves  $(9-3.5)/(15-6)$  or  $5.5/9$  i.e. 61% of the established treatment effect over no intervention (greater than the 50% minimum usually required by regulatory authorities for non-inferiority studies). At 90% power and using a one-sided 2.5% level of significance (equivalent to a two-sided 5%) level we would need to randomise 1936 participants in a fixed sample approach. We prefer to adopt a group sequential approach, giving 4 equally spaced formal interim analyses for efficacy (at 25%, 50%, 75% and a final analysis at 100% of the information) and one formal interim analysis for futility at 50% information. This flexibility to stop early on either efficacy or futility only marginally increases the maximum sample size to 2012 (4% increase, using East 6.3, Cytel Corporation 2014), a flexibility which is useful given the quality, relevance and uncertainty of the evidence base informing the sample size assumptions. If we conservatively allow for 10% loss to follow up, we would need to randomise no more than 2236 in total.

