## 1.2 EVIDENCE EXPLAINING WHY THIS RESEARCH IS NEEDED NOW

Recent meta-analysis considering VTE rates in surgical patients receiving pharmaco-prophylaxis and GCS compared with pharmaco-prophylaxis alone (8), while containing a number of methodological shortcomings, concluded that evidence concerning "adding compression to anticoagulation reduces VTE risk is of low quality." To address some of the shortcomings, a systematic review has been undertaken aiming to summarise and assess the quality of existing evidence concerning the benefits of GCS in addition to prophylactic dose pharmaco-prophylaxis in inpatients across all surgical specialties, including orthopaedics (9). Inclusion criteria were: RCTs published within the last 10 years, surgical inpatients, a study arm examining prophylactic dose pharmacological thromboprophylaxis alone (including low molecular weight heparin, fondaparinux, or unfractionated heparin), a study arm examining prophylactic dose pharmacological thromboprophylaxis in conjunction with GCS, and outcome of VTE. A heterogeneity analysis was conducted concerning rates of VTE in the included study arms. 1025 articles were screened of which 27 RCTs were included (7,11-33). Six RCT study arms included patients with GCS in conjunction with prophylactic dose pharmacological thromboprophylaxis, whilst 22 RCT study arms included patients treated with prophylactic dose pharmacological thromboprophylaxis alone. Only one RCT had both its' study arms included in the systematic review. Total number of patients that received prophylactic pharmacological thromboprophylaxis alone was 12,481. Of these patients, 1,292 (10.4%) suffered VTE. The total number of patients that received GCS in

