conjunction with prophylactic pharmacological thromboprophylaxis was 1,283. Of these patients, 75 had VTE (5.8%). Heterogeneity analysis demonstrated that the results of included study arms were significantly heterogeneous, precluding calculation of the usual meta-analytic summary estimates. The additional benefit of GCS to pharmacological thromboprophylaxis in surgical inpatients is not clear based on existing data. There is sufficient uncertainty to conduct a trial to examine whether GCS further reduces VTE incidence in surgical patients receiving prophylactic dose LMWH. Overall, systematic review and meta-analysis data have highlighted the current lack of evidence for the additional benefit of GCS over and above the benefit of LMWH in surgical patients (8,9); further trials to address this matter have been advised (3).

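### The claim that the 3.5-point margin preserves 61% of the effect uses no prophylaxis as its reference, although both arms receive LMWH; the protocol has no established stocking effect from which a preserved share could be claimed

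*Protocol*

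**What the plan says.** Section 7.1.1 sets out the planning values. The combined arm is assumed to have a 90-day VTE proportion of 6%, and the margin follows: "We have set the non-inferiority margin at 3.5% (i.e. a pharmacological alone rate under the null hypothesis of not more than 9.5" per cent. Two grounds are given. The first is clinical: clinicians would not accept an absolute worsening above 3.5 points relative to combination therapy. The second is a preserved-effect argument: the margin keeps "61% of the established treatment effect over no intervention (greater than the 50% minimum usually required by regulatory authorities for non-inferiority studies". The untreated rate in that calculation is introduced with "Historically, we believe the systematic review supports an untreated rate of at least 15" per cent.

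Sections 1.2, 2.1 and 6.1 state that every participant receives prophylactic-dose LMWH. The arms differ only in whether stockings are added.

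Section 1.2 summarises the review of pharmacoprophylaxis with and without stockings. For pharmacoprophylaxis alone: "Total number of patients that received prophylactic pharmacological thromboprophylaxis alone was 12,481. Of these patients, 1,292 (10.4%) suffered VTE". For stockings added, the number treated in "conjunction with prophylactic pharmacological thromboprophylaxis was 1,283. Of these patients, 75 had VTE (5.8" per cent). The same section says that only one trial contributed both arms, that heterogeneity ruled out a summary estimate, and that the added benefit of stockings is unclear.

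Section 7.1.2 then lists 4.0% as the detectable margin for subpopulation 4 (912 randomised, assumed rate 3.6%). It gives no preserved-effect or clinical argument for that figure.

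**The concern.** A preserved fraction shows that a non-inferior treatment keeps a known share of the benefit that is being put at risk. Here the treatment being removed is the stockings; LMWH stays in both arms. The fall from 15% to 6% contains the whole LMWH effect, which neither arm can lose. Counting it in the denominator makes the margin look stricter than it is for the question the trial asks.

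This matters because the Impact section expects the result to shape guidance and possibly remove the need for stockings in this group. A reader told that 61% of the effect is protected, above a regulatory minimum, would take a positive result to mean that most of the benefit of stockings had been shown to be retained. The figure does not support that.

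**Working it through.** **1. Reproduce the plan's figures.**

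- Preserved share = 1 − margin/(reference rate − combined-arm rate) = 1 − 3.5/(15 − 6) = 5.5/9 = 61.1%. This matches the stated 61%.
- Fixed-sample size at 6% in both arms, margin 3.5 points, one-sided 2.5%, 90% power: 2 × 0.06 × 0.94 × (1.960 + 1.282)² / 0.035² gives 968 per arm, 1936 in total. This matches. The group sequential maximum of 2012 divided by 0.9 gives 2236, which also matches.

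There is no arithmetic error. The question is which reference rate belongs in the formula.

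**2. Identify the effect at risk.** The test arm is LMWH alone and the comparator is LMWH plus stockings. The relevant denominator is the VTE rate on LMWH alone minus the rate on LMWH plus stockings.

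**3. Look for that increment in the protocol.** The only figures are those of the review in section 1.2:

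- Without stockings: 1,292/12,481 = 10.35%.
- With stockings: 75/1,283 = 5.85%.
- Difference: 4.51 points from the counts, 4.6 from the rounded percentages.

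**4. Put it into the same formula (illustrative).**

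| Increment used | Share preserved at 3.5 points |
|---|---|
| 4.6 (rounded rates) | 1 − 3.5/4.6 = 24% |
| 4.51 (counts) | 1 − 3.5/4.51 = 22% |
| 4.4 (10.4% minus the planning rate of 6%) | 1 − 3.5/4.4 = 20% |
| 3.1 (lower naive 95% limit) | −12% |
| 5.9 (upper naive 95% limit) | 41% |

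The naive interval is 4.51 ± 1.96 × 0.71 points. It treats the pooled counts as two simple samples and ignores variation between trials, so it is too narrow.

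**5. What would reach 50%?** 1 − 3.5/increment ≥ 0.5 requires an increment of at least 7 points. Nothing in the protocol suggests one that large.

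**6. Check the source of the 15%.** The review in section 1.2 took arms on pharmacoprophylaxis alone and arms on pharmacoprophylaxis with stockings. No untreated arm is described, so the document does not show where the 15% comes from.

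**7. Where the 4.0 points comes from.** 2 × 0.036 × 0.964 × (1.960 + 1.282)² / 0.04² gives 456 per arm, 912 in total. The margin and the sample size fit each other exactly, with no allowance for loss. That agrees with the label in section 7.1.2: 4.0 is what 912 patients can detect at a 3.6% rate.

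**The case against.** The strongest reply has four parts.

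- *The 22-24% is weaker evidence than the figure it would replace.* It subtracts crude totals across different trials, which the review itself declined to summarise. This stands. A reader might infer that the margin is known to preserve only about a quarter of the stocking effect; the documents do not support that. The sound statement is that no increment is established, so no preserved share can be claimed. The same point removes support for the 61%.
- *The margin has a second ground.* The clinical-tolerance argument for 3.5 points is independent, and nothing here refutes it.
- *Section 7.1.1 is historical.* Its sample size was replaced after January 2018. It remains, however, the only justification of a margin in the current protocol.
- *No preserved-effect claim is made for 4.0 points.* Correct. A reader might set 13% (1 − 4.0/4.6) against the stated 61%, but that would attribute to 4.0 a claim the protocol never makes.

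Two further inferences also go too far. One is that half the crude increment, 2.3 points, should become a benchmark. It would rest on the same unusable contrast, and in subpopulation 4 the power to exclude it is only about 46% (0.023/0.0123 − 1.96 = −0.10 on the normal scale); section 7.2.2 plans separate analyses, not a pooled one. The other is that the review cannot support 15%. Section 7.1.1 gives no citation for the review it means, and section 1.1 cites others, so the fair statement is that the support is not shown.

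**Conclusion.** The claim is wrong as written, because of its reference and not its arithmetic. The 61% describes combined prophylaxis against none, a contrast the trial does not test, so the comparison with a 50% minimum does not apply to the question asked. That conclusion needs only the fact that LMWH is given in both arms.

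The size is less certain. If the crude review contrast were usable, 3.5 points would preserve about 22-24%, and no more than 41% anywhere in the naive interval. A smaller true increment would lower the share further. These numbers illustrate the direction and do not estimate a known effect.

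The 3.5 points can still stand on clinical tolerance. The 4.0 points cannot borrow that support, since it exceeds the worsening that section 7.1.1 says clinicians would not accept. A non-inferior result would show that LMWH alone is not worse by more than the margin; it would not show that stockings add no benefit.

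**What to change.** In section 7.1:

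1. Withdraw the 61% figure and the comparison with a 50% minimum.
2. State that no preserved fraction of the stocking effect can be claimed, because its increment over LMWH is not established. If the 22-24% is quoted, label it illustrative and give the heterogeneity caveat from section 1.2.
3. Rest the 3.5 points on the clinical-tolerance ground alone.
4. State that the 4.0 points in section 7.1.2 is only a detectable difference, has no preserved-effect basis, and exceeds the stated 3.5-point tolerance.
5. Limit a positive conclusion to LMWH alone being not worse by more than the stated number of points, and align the Impact section with that.

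The cost is protocol wording, carried into the SAP and the final report wherever they repeat the claim. It needs no new analysis, data or patients.
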